One cycle is defined as 28 days (a minimum of 26 days and a maximum of 31 days). The treatment period for LY2157299 must be a minimum of 10 days and a maximum of 14 days (for Parts A, B, C and D) and 21 days (for Part E); the “off-treatment” period can vary to ensure an overall cycle length of 26 to 31 days). In extenuating circumstances, the “on study drug” window for LY2157299 is allowable from Day 10 to Day 14. (In Part C and D safety lead-in Cycle 1, patients must have received 14 days of LY2157299 treatment). For Part E Cycle 1, all patients must receive 21 days of treatment, followed by 7 days off treatment. If patients are not evaluable for DLT assessment and/or PK in Cycle 1 of Part C or Part D safety lead-in, or Cycle 1 Part E, the patients will be replaced.

Per patient, the screening period is no more than 4 weeks or 28 days before the first dose of LY2157299; the planned treatment duration is 6 cycles or approximately 24 weeks, but patients may continue to receive study drug if they are still benefiting from treatment in the opinion of the investigator and Lilly physician. Follow-up visits will occur approximately 30 days after the last day of study treatment and subsequently approximately every 60 days (approximately 2 months [± 7 days]).

In case of the occurrence of severe toxicities in later cycles in patients treated with either LY2157299 monotherapy or LY2157299 in combination with ramucirumab or sorafenib, the sponsor will review and choose a lower dose or discontinue the patient, if necessary.

The final analysis for Parts A and B will be conducted after the study objectives for these 2 parts have been met. This is likely to be after approximately 30 deaths have occurred in Part B in order to have a reasonable estimate of overall survival in this patient group (AFP <1.5x ULN).

Part C will be considered complete and the final analysis initiated once 85% of events for survival analysis in the expanded cohort in Part C have occurred.

Part D will be considered complete and the final analysis initiated after the last patient has discontinued from study treatment and completed at least the 30-day follow-up visit [Visit 801].

Part E will be considered complete and the final analysis initiated after the last patient has discontinued from study treatment and completed at least the 30-day follow-up visit [Visit 801].

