9.1.4. Part E

In Part E, LY2157299 will be administered orally at 150 mg BID for 21 days followed by 7 days off. A cycle is defined as 28 days. Section 9.1.5.1 details the DLT criteria that will be used. [Table JBAK.6](#) shows the proposed dose level and schedule for Part E.

Table JBAK.6. Treatment Regimen for Part E

Dose	Schedule	Time of Day
LY2157299 150 mg BID	Daily by oral administration 21 days on/7days off	Morning and evening for 21 days and then paused for 7 days

Abbreviations: BID = twice daily.

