9.9. Treatment Compliance

Patient compliance with study medication will be assessed at each visit. Compliance will be assessed by direct questioning, review of diary, and counting returned tablets. Deviations from the prescribed dosage regimen should be recorded in the "Study treatment: modifications" form.

For patients who are significantly noncompliant (<80% or >120% of expected study drug taken in a visit interval), investigative sites must counsel patients on the importance of study drug compliance and drug accountability. Patients who are consistently out of the compliance range may be discontinued. A Lilly representative should be contacted upon the second instance of treatment noncompliance.

The following procedures will be employed to assure appropriate drug accountability:

- Drug accountability will be emphasized at the start-up meeting.
- Drug accountability will be monitored throughout the study.
- Each patient should be instructed to return all study-drug packaging and unused material to the study site at each visit. The study site will keep a record of all drug dispensed to and returned by the patients throughout the study. Study site personnel will return or destroy (as requested) all unused study drug for all patients.
- Patients will keep a study diary to document that they are taking LY2157299 and sorafenib (if applicable) correctly.

Ramucirumab in Part D will be administered intravenously at the investigational site, under the direction of the investigator. As a result, a patient's compliance with study drug administration is ensured.

10. Efficacy, Health Outcome/Quality of Life Measures, Safety Evaluations, Sample Collection and Testing (Standard Laboratory Testing, Pharmacokinetics, Biomarker Analysis), and Appropriateness of Measurements

Refer to the Study Schedule in [Attachment 1](#) for study procedures and their timing.

Terms used to describe the study periods are defined below:

- **Baseline/Visit 0:** From the time of screening to first study treatment (or discontinuation, if no treatment is given)
- **Treatment Start:** First day of study treatment
- **Study Treatment Period:** Time from treatment start to discontinuation from study treatment
- **Discontinuation from Study Treatment:** The day the patient discontinues study treatment (summary visit)
 - **Applies to patients in extension period, too**

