12.2.7. Treatment Compliance

A summary of treatment compliance will be generated using information from drug accountability records and the patient diary. A patient will be considered compliant with the study-therapy protocol if pill counts indicate the patient took at least 80% of LY2157299 during the preceding cycle of study therapy (refer to Section 9.9).

An attempt may be made to determine how compliance to study treatment relates to observed study-related outcome.

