Abbreviations: AFP = alpha-fetoprotein; aPTT = activated partial prothrombin time; C = cycle; CLIP = Cancer of the Liver Italian Program; CT = computerized tomography; CTCAE = Common Terminology Criteria for Adverse Events; ECG = electrocardiogram; FACT = Functional Assessment of Cancer Therapy; INR = international normalized ratio; MAP = multi-analyte panel; MRI = magnetic resonance imaging; PGx = pharmacogenomics; PIVKA II = prothrombin induced by vitamin K absence; PK = pharmacokinetic; PT = prothrombin time; TGF-β = transforming growth factor beta.

- a If drug-related toxicity is present 30 days after last cycle of study drug, patients must be followed up approximately every 30 days until toxicity resolution, stabilization, another therapy is initiated, or death.
- b If the patient has clinically significant cardiac findings at discontinuation (V801), echocardiography with Doppler, ECG, and ECG chemistry will be repeated every 2 months for 6 months (V803, V804, and V805). If there are no cardiac findings at discontinuation (V801), 1 more echocardiography with Doppler, ECG, and ECG chemistry will be performed after 2 months (V802) unless a patient is receiving another treatment (see Section 10.2.4).
- c If there were no clinically significant findings at the last assessment conducted within the 30 days following discontinuation and the patient has started another treatment, Visit 801 CT scan or chest MRI with contrast will not be performed.
- d Repeat radiological scans at study discontinuation may be omitted if a patient has objective disease progression or if imaging has been performed in the previous 3 to 6 weeks.
- e For details, see Attachment 4. PK sampling will be performed on Cycle 1, with a predose sample on Day 1 of Cycle 2 and all subsequent cycles.
- f Follow-up consists of Visit 802 and all subsequent visits (60 days ±7 days)
- g Echocardiography with Doppler can be performed up to 3 days prior to Day 1.
- h Child-Pugh, BCLC, and CLIP assessment procedures can be found in Attachment 5, Attachment 6, and Attachment 7, respectively.
- i To be performed predose LY2157299.
- j A delay at the start of a cycle (Day 1) of no more than 3 days, because of holidays, weekends, inclement weather, or other justifiable events, will be permitted and not counted as a protocol violation.
- k In extenuating circumstances, the ‘on study drug’ window is allowable from Day 10 to Day 14.

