Abbreviations: AFP = alpha-fetoprotein; aPTT = activated partial prothrombin time; C = cycle; CLIP = Cancer of the Liver Italian Program; CT = computerized tomography; CTCAE = Common Terminology Criteria for Adverse Events; D = Day; ECG = electrocardiogram; FACT = Functional Assessment of Cancer Therapy; INR = international normalized ratio; MAP = multi-analyte panel; MRI = magnetic resonance imaging; PGx = pharmacogenomics; PIVKA II = prothrombin induced by vitamin K absence; PK = pharmacokinetic; PT = prothrombin time; TGF-β = transforming growth factor beta.

- a If drug-related toxicity is present 30 days after last cycle of study drug, patients must be followed up approximately every 30 days until toxicity resolution, stabilization, another therapy is initiated, or death.
- b If the patient has clinically significant cardiac findings at discontinuation (V801), echocardiography with Doppler, ECG, and ECG chemistry will be repeated every 2 months for 6 months (V803, V804, and V805). If there are no cardiac findings at discontinuation (V801), 1 more echocardiography with Doppler, ECG, and ECG chemistry will be performed after 2 months (V802) unless a patient is receiving another treatment (see Section 10.2.4).
- c If there were no clinically significant findings at the last assessment conducted within the 30 days following discontinuation and the patient has started another treatment, Visit 801 CT scan or chest MRI with contrast will not be performed.
- d Repeat radiological scans at study discontinuation may be omitted if a patient has objective disease progression or if imaging has been performed in the previous 3 to 6 weeks.
- e For details, see Attachment 4. PK sampling will be performed on Cycle 1, with a predose sample on Day 1 of Cycle 2 and all subsequent cycles.
- f Follow-up consists of Visit 802 and all subsequent visits (60 days ±7 days). All patients will be followed for OS until study completion.
- g Echocardiogram with Doppler can be performed up to 3 days prior to Day 1.
- h Child-Pugh, BCLC, and CLIP assessment procedures can be found in Attachment 5, Attachment 6, and Attachment 7, respectively.
- i To be performed predose LY2157299.
- j A delay at the start of a cycle (Day 1) of no more than 3 days, because of holidays, weekends, inclement weather, or other justifiable events, will be permitted and not counted as a protocol violation.

- k In extenuating circumstances, the 'on study drug' window is allowable from Day 10 to Day 14.

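### In extenuating circumstances, Part E patients may stop drug between Day 10 and Day 14 from Cycle 2 on, because a window written for 14-day dosing was kept for a 21-day regimen

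*Protocol*

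**What the plan says.** Protocol Section 9.1.4 sets the Part E regimen: "LY2157299 will be administered orally at 150 mg BID for 21 days followed by 7 days off". Table JBAK.6 repeats it without any note on shortened dosing. Tables JBAK.3, JBAK.4 and JBAK.5, for the 14-day parts, each carry a note allowing a Day 10 to Day 14 window.

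The Part E schedule in Attachment 1 does carry the window. Footnote k is attached to the Day 14 columns of Cycle 2 and of Cycle 3 onward, and reads: "In extenuating circumstances, the 'on study drug' window is allowable from Day 10 to Day 14". Footnote k of the Parts A and B schedule has the same wording.

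Under All Study Parts, Protocol Section 7.1 makes three relevant statements:

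- Limits on dosing length per cycle are given as follows: "a minimum of 10 days and a maximum of 14 days (for Parts A, B, C and D) and 21 days (for Part E").
- In extenuating circumstances the on-drug "window for LY2157299 is allowable from Day 10 to Day 14". This sentence is not restricted to Parts A to D.
- "For Part E Cycle 1, all patients must receive 21 days of treatment, followed by 7 days off treatment". No matching rule is given for Part E Cycle 2 or later.

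**The concern.** In the 14-day parts the window ends on the last planned dosing day, so it lets a patient stop up to four days early. In Part E the last planned dosing day is Day 21. The same window therefore ends a week before dosing should finish, and even its latest day is a substantial cut.

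Protocol Section 5.1.10 says Part E was added to improve on 14-on/14-off by lengthening time on target. Section 7.2 plans to compare its safety, PK and efficacy with the 14-day schedule. Section 7.1 adds that cardiovascular effects could appear after the dose-limiting toxicity (DLT) period, so later cycles matter for safety as well. A cycle shortened under footnote k loses the extra exposure that Part E is meant to study. With up to about 23 patients planned, a few such cycles could blur the later-cycle picture. Sites also hold two instructions that disagree, one in the treatment section and one in the schedule.

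**Working it through.** The plan gives no figure of its own here, so there is nothing to reproduce. The check is a comparison of texts and simple division.

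**Inputs**
- Planned Part E dosing: 21 days per cycle at 300 mg/day (Section 9.1.4, Table JBAK.6).
- Permitted window: Day 10 to Day 14 (Part E footnote k; Section 7.1).
- Comparison schedule: 14 days per cycle at 300 mg/day (Table JBAK.3, Cohort 2 and Part B).
- Per-cycle compliance line in Section 12.2.7: a patient is compliant who "took at least 80% of LY2157299 during the preceding cycle of study therapy".
- Planned treatment: 6 cycles (Section 7.1).

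**Share of planned Part E days** = days taken / 21
- Day 10: 10/21 = 47.6%; 10 × 300 = 3000 mg
- Day 11: 11/21 = 52.4%
- Day 12: 12/21 = 57.1%
- Day 13: 13/21 = 61.9%
- Day 14: 14/21 = 66.7%; 14 × 300 = 4200 mg
- Full cycle: 21 × 300 = 6300 mg

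A full 14-on/14-off cycle gives 14 × 300 = 4200 mg. The longest stop in the window equals that, and every earlier stop falls below it.

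**The same window in the 14-day parts** = days taken / 14
- Day 10: 10/14 = 71.4%
- Day 14: 14/14 = 100%

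**What a window for 21-day dosing might look like**
- Scaling the existing ratio: 10/14 × 21 = 15, so Day 15 to Day 21.
- Meeting the 80% line per cycle: 0.80 × 21 = 16.8, so at least 17 days; 17/21 = 81.0%, giving Day 17 to Day 21.

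**Does other text override footnote k?**
- Section 7.1 fixes 21 days for Part E in Cycle 1 only. Of the 6 planned cycles, 5 fall outside that rule.
- The only numeric minimum in Section 7.1 is 10 days.
- Section 9.1.4 gives the regimen but no minimum.
- Section 9.5.1 allows a changed Part E schedule after toxicity, following discussion with the sponsor's physician. Footnote k requires no such discussion.

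Nothing found removes the window from Part E Cycle 2 onward.

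**The case against.** The best case against this is that footnote k is a copying leftover that no site would take as a dosing rule. Section 7.1 separates 14 days for Parts A to D from 21 days for Part E, and Table JBAK.6 omits the window. The sponsor may well have meant Part E to have none. That is plausible as to intent, but it does not settle the text. If 21 days were fixed in every Part E cycle, the separate Cycle 1 rule would be redundant and footnote k would contradict it. Nor is it only a visit window: it is worded as time on study drug, and Section 7.1 places it beside the treatment-period limits.

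The points about consequence stand:
- Part E Cycle 1 must run 21 days, with replacement of patients not evaluable for DLT or PK.
- The main PK profile is taken in Cycle 1.
- Section 12.1 plans no formal efficacy testing.
- Section 9.9 requires dosing deviations to be recorded.
- A shorter cycle moves exposure towards a schedule the protocol describes as well tolerated.
- Section 9.5.1 already allows some later-cycle departures, so removing footnote k would not guarantee 21 days.

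Three stronger readings are tempting but not supported:
- **That 10 to 14 days is generally allowed from Cycle 2.** The window is conditional on extenuating circumstances. The 10-day minimum carries no such condition, but its application to Part E is ambiguous.
- **That every permitted stop is noncompliance.** Section 9.9 uses "<80% or >120% of expected study drug taken in a visit interval", and all five stops are below 80% of 21 days. However, the documents do not say whether expected drug stays at 21 days after a permitted stop.
- **That the SAP miscounts Part E dose intensity by using 14 planned days.** The supplied SAP is aligned with Amendment (c) and predates Part E. Section 12.2.8 promises a version 4 before the first Part E dose, and that version is not supplied.

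**Conclusion.** The point holds in a limited form. In extenuating circumstances, the current protocol lets a Part E patient stop drug between Day 10 and Day 14 in any cycle after the first. Such a cycle delivers 48% to 67% of planned days and no more than a 14-on/14-off cycle. This conflicts with the regimen in Section 9.1.4 and Table JBAK.6 and works against the purpose of Part E.

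The conclusion rests on reading footnote k and the Section 7.1 sentence as written, since neither excludes Part E. The percentages assume only the 21 planned days and the stated daily dose. What is exposed is later-cycle exposure, tolerability and efficacy data. How often the window would be used cannot be judged from the documents. It should be corrected because it is an operative dosing instruction and the correction is nearly free. It does not undermine the Cycle 1 DLT or PK assessments.

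**What to change.** 1. Delete footnote k from the Part E schedule in Attachment 1.
2. In Section 7.1, confine both the Day 10 to Day 14 sentence and the 10-day minimum to Parts A to D.
3. State a Part E minimum or window for Cycle 2 onward in Section 7.1, with a matching note under Table JBAK.6. Without this step, steps 1 and 2 leave Part E with no stated minimum after Cycle 1. Day 17 to Day 21 is one option and meets the 80% line per cycle.
4. Leave toxicity-driven changes to Section 9.5.1.

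When setting the new window, say how expected drug is counted if it is used. Day 17 meets the per-cycle line in Section 12.2.7, but Section 9.9 works per visit interval. With a Day 14 visit and expected drug kept at 7 days for Days 15 to 21, a Day 17 stop would give 3/7 = 43% in that interval.

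The cost is wording: one footnote, two sentences in Section 7.1, one new Part E rule and its table note, plus a line on counting. Visits, sampling and sample size do not change.

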Attachment 2. Protocol JBAK Clinical Laboratory Tests

Clinical Laboratory Tests

Hematology^a	Clinical Chemistry^b
Hemoglobin	Total bilirubin
Erythrocyte count (RBC)	Direct bilirubin
Leukocytes (WBC)	Total Protein
Neutrophils, segmented + bands	Alkaline phosphatase
Lymphocytes	LDH
Monocytes	Creatinine kinase (CK)
Eosinophils	ALT/SGPT
Basophils	AST/SGOT
Platelets	Blood urea nitrogen (BUN)
	Creatinine
Immunophenotype ^b	Uric acid
	Calcium
Urinalysis^a	Glucose, random (nonfasting)
Specific gravity	Albumin
pH	Cholesterol
Protein	Phosphorus
Glucose	Sodium
Ketones	Potassium
Blood	Magnesium
Leukocyte esterase	
	AFP ^b
ECG Chemistry^b	AFP L3 ^b
Lipase	PIVKA II ^b
Thyroid Stimulating Hormone (TSH)	E-cadherin ^b
Tri-iodothyronine (T3)	TGF- β +PF4 ^b
Thyroxine (T4)	
Calcium ^c	aPPT/PT/INR ^b
Glucose, random (nonfasting) ^c	
Albumin ^c	Fibrotest ^b
Phosphorus ^c	
Sodium ^c	Urine C-terminal telopeptides of Type 1 Collagen ^b
Potassium ^c	
Magnesium ^c	Serum Pregnancy Test (females only) ^a
Special Chemistry^b	
Cystatin C	
Troponin I	
BNP	
High-sensitivity C-reactive protein (hs-CRP)	

Abbreviations: AFP = alpha-fetoprotein; ALT = alanine aminotransaminase; aPTT = activated partial prothrombin time; AST = aspartate aminotransferase; BNP = brain natriuretic peptide; ECG = electrocardiogram; INR = international normalized ratio; LDH = Lactate Dehydrogenase; SGOT = serum glutamic oxaloacetic transaminase; SGPT = serum glutamic pyruvic transaminase; WBC = white blood cells; PIVKA II = prothrombin induced by vitamin K absence.

- a All samples will be discarded within 60 days of validated test results. Validation will occur at the time of initial testing. All these tests will be performed at a local or investigator-designated laboratory, with the exception of immunophenotype.
- b All samples will be discarded within 60 days of validated test results. Validation will occur at the time of initial testing. All these tests will be performed at a Lilly-designated laboratory. Tests will be performed at a local laboratory if performed during the treatment extension period.
- c Test not performed if both chemistry and ECG chemistry are required. See [Attachment 1](#).

Attachment 3. Protocol JBAK ECOG Performance Status

ECOG Performance Status

Activity Status	Description
0	Fully active, able to carry on all predisease performance without restriction
1	Restricted in physically strenuous activity but ambulatory and able to carry out work of a light or sedentary nature, for example, light house work, office work
2	Ambulatory and capable of all self care but unable to carry out any work activities. Up and about more than 50% of waking hours
3	Capable of only limited self care. Confined to bed or chair more than 50% of waking hours
4	Completely disabled. Cannot carry on any self care. Totally confined to bed or chair
5	Dead

Source: Oken MM, Creech RH, Tormey DC, Horton J, Davis TE, McFadden ET, Carbone PP. *Am J Clin Oncol.* 1982;Dec;5(6):649-655.

Attachment 4. Protocol JBAK Pharmacokinetic Sampling Instructions

Sparse PK Sampling Schedule Parts A and B

Sample Number	Cycle	Day	Sampling Windows for PK
1	1	1	Predose ^a
2	1	1	0.5-2 hours
3	1	14	Predose ^a
4	1	14	0.5-2 hours
5 ^b	1	14	3-5 hours
6 ^b	1	15	Morning
7	1	22	Morning
8	2	1	Predose ^a
9	3, n	1	Predose ^a

Abbreviations: n = cycle number \geq Cycle 4; PK = pharmacokinetic.

^a The predose sample has to be taken before receiving any LY2157299.

^b For patients who will have a Day 15 PK sample taken, their evening dose of LY2157299 on Day 14 should be omitted.

Part C Sampling Schedule for Safety Lead-in Cohorts

Day	LY2157299 + Sorafenib Dosing Schedule	Sampling Times	
		Pharmacokinetics (LY2157299)	Pharmacokinetics (Sorafenib)
Cycle 1 Day 1 (Day at which sorafenib and LY2157299 are combined)	Both drugs as per Section 9	Predose ^a	Predose ^a
		0.5 h after dose	0.5 h after dose
		2 h after dose	2 h after dose
		3 h after dose	3 h after dose
		6 h after dose	6 h after dose
Cycle 1 Day 8	Both drugs as per Section 9	Predose ^a	Predose ^a
Cycle 1 Day 14 ^b (last day of LY2157299 dosing)	Both drugs as per Section 9	Predose ^a	Predose ^a
		0.5 h after dose	0.5 h after dose
		2 h after dose	2 h after dose
		3 h after dose	3 h after dose
		6 h after dose	6 h after dose
Cycle 1 Day 15 ^b	Sorafenib only as per Section 9	Morning (before sorafenib is taken)	Morning (before sorafenib is taken)
Cycle 1 Day 22	Sorafenib only as per Section 9		Predose ^a
			0.5 h after dose
			2 h after dose
			3 h after dose
			6 h after dose
Cycle 1 Day 23	Sorafenib only as per Section 9		Morning PK (predose)
Cycle 2 Day 1	Both drugs as per Section 9	Predose ^a	Predose ^a
Cycle 2 Day 1	Both drugs as per Section 9	0.5-2 hours	0.5-2 h
Cycle 2, Day 14 ^b	Both drugs as per Section 9	Predose ^a	Predose ^a
Cycle 2, Day 14 ^b	Both drugs as per Section 9	0.5-2 hours	0.5-2 h
Cycle 2, Day 14 ^b	Both drugs as per Section 9	3-5 hours	3-5 h
Cycle 2, Day 15 ^b	Sorafenib only as per Section 9	Morning (before sorafenib is taken)	Predose ^a
Cycle 3, Day 1	Both drugs as per Section 9	Predose ^a	Predose ^a
Cycle 4, n, Day 1	Both drugs as per Section 9	Predose ^a	Predose ^a

Abbreviations: h = hour(s); n = cycle number \geq Cycle 4; PK = pharmacokinetic.

^a The predose sample has to be taken before receiving any LY2157299 or sorafenib.

^b For patients who will have a Day 15 PK sample taken, their evening dose of LY2157299 on Day 14 should be omitted.

Part C Sampling Schedule for LY2157299 and Sorafenib in Expansion Cohort

Sample Number	Cycle	Day	Sampling Windows for PK
1	1	1	Predose ^a
2	1	1	0.5-2 hours
3	1	14	Predose ^a
4	1	14	0.5-2 hours
5 ^b	1	14	3-5 hours
6 ^b	1	15	Morning
7	1	22	Morning
8	2	1	Predose ^a
9	3, n	1	Predose ^a

Abbreviation: PK = pharmacokinetic.

a The predose sample has to be taken before receiving any LY2157299 or sorafenib.

b For patients who will have a Day 15 PK sample taken, their evening dose of LY2157299 on Day 14 should be omitted.

Part D Sampling Schedule

Day	LY2157299 + RAM Dosing Schedule	Pharmacokinetic Sampling Times (LY2157299) plasma	Pharmacokinetic Sampling Times (RAM) serum
Cycle 1 Day 1 (Day at which RAM and LY2157299 are combined)	Both drugs as per Section 9	Predose ^a	Predose ^a
		1.5-3 h after LY2157299 dose	End of RAM infusion
Cycle 1 Day 14 ^b (last day of LY2157299 dosing)	LY2157299 as per Section 9	Predose ^a	
		0.5 h after dose	
		2 h after dose	
		3 h after dose	
		6 h after dose	
Cycle 1 Day 15 ^b	RAM only as per Section 9	Morning (before RAM is taken)	Predose
Cycle 1 Day 15	RAM only as per Section 9		End of RAM infusion
Cycle 2 Day 1	Both drugs as per Section 9	Predose ^a	Predose ^a
		1.5-3 hours after dose (LY)	End of RAM infusion
Cycle 2, Day 14 ^b	LY2157299 as per Section 9	Predose ^a	
		0.5-2 hours	
		3-5 hours	
Cycle 2, Day 15 ^b	RAM only as per Section 9	Morning (before RAM is taken)	Predose
Cycle 2 Day 15	RAM only as per Section 9		End of RAM infusion
Cycle 3, Day 1	Both drugs as per Section 9	Predose ^a	Predose ^a
Cycle 4, n, Day 1	Both drugs as per Section 9	Predose ^a	Predose ^a

Abbreviations: h = hour(s); LY = LY2157299; n = cycle number \geq Cycle 4; PK = pharmacokinetic;
RAM = ramucirumab.

a The predose sample has to be taken before receiving any LY2157299 or ramucirumab.

b For patients who will have a Day 15 PK sample taken, their evening dose of LY2157299 on Day 14 should be omitted.

Part E Sampling Schedule for LY2157299

Sample Number	Cycle	Day	Sampling Windows for PK
1	1	1	Predose ^a
2	1	1	0.5-2 hours
3	1	21	Predose ^a
4	1	21	0.5-2 hours
5 ^b	1	21	3-5 hours
6 ^b	1	22	Morning
7	2	1	Predose ^a
8	3 - n	1	Predose ^a

Abbreviation: PK = pharmacokinetic.

a The predose sample should be taken before the patient receives any LY2157299.

b For patients who will have a Day 22 PK sample taken, the evening dose of LY2157299 on Day 21 should be omitted.

